Our long term goal is to develop a phase III study in response to a specific NIH FOA using high content screening of leucocyte LC3 puncta scores, qRT-PCR transcription factor EB (TFEB) scores, and assays of total DNA methylation and galectin-3, to gauge the magnitude of metformin's effects on autophagy and cell senescence as markers of aging in adults with prediabetes. This study will provide preliminary data for such a proposal and will also fill a knowledge gap regarding the use of validated biomarkers in this field. It will also contribute significantly to the overall anti-aging literature. The primary objective of this proposal is to validate the autophagy experimental design in humans by using leucocyte LC3, TFEB, Galectin-3, and total methylation of DNA scores as markers of autophagy activity and cell senescence.

1.2. State the hypotheses to be tested.

AIM 1: Demonstrate that metformin therapy will increase cellular autophagy as an inverse correlate of aging as measured by increases in LC3 and TFEB scores.

Hypothesis 1: In addition to beneficial effects on glycemia, body weight, and body composition, metformin therapy exerts beneficial effects on surrogate measures of autophagy and aging.

Primary outcome: Increased levels of LC3 in leukocytes.

AIM 2: Demonstrate that metformin therapy will mitigate evidence of aging as measured by increased DNA methylation and decreased serum galectin 3 among adults with prediabetes.

Hypothesis 2: Metformin therapy exerts beneficial effects on DNA methylation as measures of aging

Primary outcome: Increased DNA methylation in leukocytes.

AIM 3: Monitor the beneficial metabolic effects of metformin in adults with prediabetes. Hypothesis 3: Metformin therapy will elicit the expected beneficial effects on glycemia, body weight, insulin resistance, and body composition demonstrated in previous studies.

Primary outcome: Decreased A1c.

2. Background

2.1. Describe the relevant prior experience and gaps in current knowledge.

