We will perform a randomized, quasi-double blind, placebo-controlled trial of metformin in adult patients with prediabetes. Inclusion criteria will comprise individuals aged 30-70 years (inclusive) with prediabetes (defined as an A1c of 5.7-6.4%) and a BMI between 27 and 40 kg/m² (inclusive). Exclusion criteria will include prior treatment with metformin or other diabetes medications, pregnancy, the presence of significant renal dysfunction (Serum Creatinine > 1.3 mg/dl for women, > 1.4 mg/dl for men), severe hepatic dysfunction (AST or ALT > 3 times the upper limit of normal), ongoing alcohol or substance abuse, inflammatory bowel disease, ongoing glucocorticoid therapy, or inability to render informed consent.

Figure 1: Anti-Aging, Pro-Autophagy Effects of Metformin in Adults with Prediabetes

PROTOCOL TITLE: A Double-Blind, Placebo-Controlled Trial of Anti-Aging, Pro-Autophagy Effects of Metformin in Adults with Prediabetes

As summarized in the accompanying **Figure 1**, all subjects will complete four study-related visits. All visits will occur within a 7-day window of the target date. At Visit 1, informed consent will be obtained, a brief medical history and physical examination will be performed, and a health-history questionnaire will be completed by the participant. Blood samples will also be obtained for eligibility criteria at this visit. Women of child-bearing age will receive a urine pregnancy test at Visit 1.

At Visit 2, randomization to placebo or active Metformin will occur. All subjects will receive standardized instruction about diet and exercise for the prevention of diabetes and will be provided with a pedometer. Participants will subsequently be instructed to attempt to walk at least 10,000 steps per day five days during each week for the 12-week duration of the study. A step diary will be provided for subjects to complete daily to collect their step data.

As shown in **Table 1**, the following data will be collected at visit two (Week 0), visit three (4 weeks), and visit four (12 weeks).

After randomization, all subjects will receive 90 days worth of study medication in the form of either Metformin or Placebo (i.e.- nearly identical Calcium carbonate

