PROTOCOL TITLE: A Double-Blind, Placebo-Controlled Trial of Anti-Aging, Pro-Autophagy Effects of Metformin in Adults with Prediabetes

Lifestyle Intervention: All study participants will be educated in the importance of lifestyle modification in a manner consistent with the Diabetes Prevention Program [122], and all subjects will be expected to follow these instructions throughout the course of the 12 week study period. Specifically, subjects will be asked to attempt to achieve a modest reduction in total calories (500-1000 kcal/d) each day [123], as is consistent with the recommendations of the American Diabetes Association [124]. We will also ask participants to approach the physical activity recommendations of the Diabetes Prevention Program by asking them to walk 10,000 steps per day at least five days per week [125]. This amount of exercise will approximate the 150 minutes of moderately strenuous exercise achieved by participants in the lifestyle intervention arm of the Diabetes Prevention Program.

Study Population:

We will recruit potential subjects with prediabetes from the Endocrinology Clinics, from the CTSC participant recruitment service, and from the UNM Prediabetes Cohort Registry. This latter registry is the result of a small CDC-sponsored study performed at UNM a few years ago that identified 104

subjects with prediabetes out of 218 at-risk subjects who were screened (HRRC # 11-422) [126]. These subjects agreed to be contacted in the event of future research involving prediabetes. We will also employ CTSC-sponsored social media to recruit for this study, if necessary. We do not anticipate much difficulty identifying subjects who are interested in participating in this study. We estimate that 50 adults at risk for diabetes will need to be screened to find 30 eligible subjects with prediabetes to enroll in this study.

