
PROTOCOL TITLE: A Double-Blind, Placebo-Controlled Trial of Anti-Aging, Pro-Autophagy Effects of Metformin in Adults with Prediabetes

Repeated Measures ANCOVA using “steps per day” and “change in body mass” as covariates.

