Primary outcome: Increased DNA methylation in leukocytes.

AIM 3: Monitor the beneficial metabolic effects of Metformin in adults with prediabetes. Hypothesis 3: Metformin therapy will elicit the expected beneficial effects on glycemia, body weight, insulin resistance, and body composition demonstrated in previous studies.

PROTOCOL TITLE: A Double-Blind, Placebo-Controlled Trial of Anti-Aging, Pro-Autophagy Effects of Metformin in Adults with Prediabetes

Primary outcome: Decreased A1c.

7.2. Describe any primary or secondary safety endpoints.

TFEB, scores, Galectin-3 levels, BMI, HOMA-IR, fasting glucose, step-counts, pill-counts, body composition, serum creatinine, history and physical exam.

7.3. Describe any exploratory endpoints.

None.

8. Research Setting

8.1. Describe the sites or locations where your research team will conduct the research.

Recruitment, screenings, health questionnaires, subject measurements and phlebotomy will be conducted at the CTSC Clinical Research Unit.

Cell purification and culturing from blood will be conducted at the CTSC T1 laboratory, while LC3 cell treatment and analysis will be conducted in the laboratories of [name], in the Department of Molecular Genetics and Microbiology, [name].

8.2. Identify where your research team will identify and recruit potential subjects.

We will recruit potential subjects with prediabetes from the Endocrinology Clinics, from the CTSC participant recruitment service, and from the UNM Prediabetes Cohort Registry (HRRC # 11-422). These latter subjects agreed to be contacted in the event of future research involving prediabetes. We will also employ CTSC-sponsored social media to recruit for this study, if necessary. We do not anticipate having difficulty identifying subjects who are interested in participating in this study. We estimate that 50 adults at risk for diabetes will need to be screened to find 30 eligible subjects with prediabetes to enroll in this study.

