Potential Challenges: If adherence to lifestyle modification is significantly different between groups, this could become an important confounder. If this occurs, we will perform a Repeated Measures ANCOVA using “steps per day” and “change in body mass” as covariates.

14. Provisions to Monitor the Data to Ensure the Safety of Subjects

This section is required when research involves more than Minimal Risk to subjects. Describe:

14.1. The entity (e.g., DMC, DSMB) or individuals (e.g., medical monitor) who will perform data and safety monitoring. Describe whether they are independent of or affiliated with the sponsor or investigator. If a DMC or DSMB is planned, describe the composition of the committee or board. Generally, a DSMB or DMC should be composed of experts in all scientific disciplines needed to analyze and interpret the data (e.g., epidemiologists, biostatisticians, subject matter experts).

We will employ [name], MD, to act as an independent monitor in the capacity of our Data Safety and Monitoring Board. [name] is independent of this study and has no vested interest in its outcome. Treatment for diabetes in this study is consistent with current standard of care, and the risks of Metformin or CaCO₃ therapy are generally mild and well characterized. We will track all study-related adverse events and prepare a report for [name] review each year prior to protocol renewal for the HRRC. We will track patients who are unable to tolerate study medication for any reason, including gastrointestinal complaints. We will also track and report all SAEs, as is standard for all clinical trials.

PROTOCOL TITLE: A Double-Blind, Placebo-Controlled Trial of Anti-Aging, Pro-Autophagy Effects of Metformin in Adults with Prediabetes

14.2. The safety information that will be collected and monitored.

Serum creatinine.

14.3. The frequency or periodicity of review of data, such as specified points in time or after a specific number of participants have been enrolled.

Safety and efficacy data will be collected at 0, 4 and 12 weeks. DSM reports will be prepared for the DSMB annually at the time of HRRC protocol renewal.

14.4. The plans for review of scientific literature and data from other sources that may inform the safety or conduct of the study.

Literature review was performed by [name], DO, and [name] from [name] lab.

14.5. The procedures for analysis and interpretation of the safety data.

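### The ANCOVA triggered by an adherence difference adjusts for post-randomisation steps and weight change, treats them as confounders, and is nowhere marked as supportive only

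*Combined protocol and SAP*

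**What the plan says.** The rule stands under Potential Challenges in Section 3.1 and again at the end of Section 13.2. The trigger reads: "If adherence to lifestyle modification is significantly different between groups, this could become an important confounder". The response is: "If this occurs, we will perform a Repeated Measures ANCOVA using “steps per day” and “change in body mass” as covariates". No test or threshold defines a significant adherence difference, and no outcome is named or excluded.

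Other parts of the protocol bear on this:

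- **Timing.** Section 3.1: "At Visit 2, randomization to placebo or active Metformin will occur". The pedometer and step diary are handed out at that visit, and change in body mass runs from it.
- **Weight as a drug effect.** Hypothesis 3 in Section 1.2 states: "Metformin therapy will elicit the expected beneficial effects on glycemia, body weight, insulin resistance, and body composition demonstrated in previous studies". Hypothesis 1 also names body weight, Table 2 expects BMI to decrease, and Section 19 mentions weight loss as a possible benefit.
- **Endpoints.** Section 7.2 lists "Galectin-3 levels, BMI, HOMA-IR, fasting glucose, step-counts, pill-counts, body composition", so BMI and step counts are themselves endpoints.
- **Lifestyle instruction.** Beyond walking, "subjects will be asked to attempt to achieve a modest reduction in total calories (500-1000 kcal/d) each day" (Section 3.1). Neither Table 1 nor Section 12.1 lists a diet record.
- **Other analyses.** The Data Analysis paragraph of Section 3.1 plans an unconditional unpaired t-test on change to Week 12 and a repeated measures ANOVA. The only analysis labelled as sensitivity is the one that carries the last value forward.

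**The concern.** A confounder must be able to influence both treatment assignment and outcome. Steps and weight change after Visit 2 cannot influence an assignment already made, so the stated reason for adjusting is wrong.

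Weight change is the more serious of the two. With no diet record, it is the only covariate that could reflect the calorie part of adherence. It cannot separate diet adherence from metformin's own action, and Section 18.1 lists reduced appetite among the drug's common side effects. Adjusting for it can remove part of the effect under study, or distort it through causes shared by weight and outcome.

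If the rule fires, the report will hold two estimates, and the confounder wording invites readers to take the adjusted one as the corrected result. The two can differ in size and in significance, and nothing says which governs.

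**Working it through.** **1. The plan's own figure.** For A1c, Sections 3.1, 5.3 and 13.2 give a change of 0.7 against 0.2, SD 0.4, 12 per arm, two-sided alpha 0.05. The standardised difference is (0.7 − 0.2)/0.4 = 1.25. Noncentral-t power with 22 df is 0.833, matching the stated 0.83 (written there as beta). This is the power of the unadjusted t-test.

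**2. Adjusting for weight change alone.** Let δ be the extra weight loss on metformin in within-arm SDs, and r the within-arm correlation of weight loss with A1c fall. Both are assumptions; Section 19 supports only a small loss. In a Week 12 change-score model the expected adjusted effect is 0.4 × (1.25 − r·δ):

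| δ | r = 0.3 | r = 0.5 |
|---|---|---|
| 0.1 | 0.488 | 0.480 |
| 0.2 | 0.476 | 0.460 |
| 0.5 | 0.440 | 0.400 |
| 1.0 | 0.380 | 0.300 |
| −0.5 (placebo loses more) | 0.560 | 0.600 |

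The unadjusted expectation is 0.500 in every row.

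**3. How often the rule fires.** Take the trigger to be a two-sided 5% t-test on steps (assumed, since none is defined). It needs an observed difference of t(0.975, 22) × √(2/12) = 0.847 SD. It fires in 5%, 22% and 65% of trials when the true step difference is 0, 0.5 and 1.0 SD.

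**4. Both covariates, fired trials only.** Further assumptions: r(steps, A1c fall) = 0.2 and r(steps, weight loss) = 0.3. With dS the true step difference and dM the extra weight loss (both metformin relative to placebo, in SDs), the expected adjusted effect is 0.4 × (1.25 − bS·dS − bM·dM), where bS = (0.2 − 0.3r)/0.91 and bM = (r − 0.06)/0.91. Simulation at 12 per arm (20 df for the adjusted model) agrees with this:

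| dS; dM; r | Mean effect, unadjusted / adjusted | Power, unadjusted / adjusted | Disagree on p<0.05 |
|---|---|---|---|
| 0; 0; 0.3 | 0.50 / 0.50 | 0.82 / 0.75 | 18% |
| 0; 0.1; 0.3 | 0.50 / 0.49 | 0.82 / 0.73 | 19% |
| 0.5; 0.2; 0.3 | 0.54 / 0.46 | 0.89 / 0.65 | 25% |
| 1.0; 0.5; 0.5 | 0.52 / 0.38 | 0.86 / 0.54 | 35% |
| −1.0; −0.5; 0.5 | 0.48 / 0.62 | 0.81 / 0.91 | 16% |

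Over dS from −1.0 to +1.0 and r of 0.3 or 0.5:

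- dM of 0.1–0.2 gives adjusted effects of 0.43–0.54, adjusted power of about 0.58–0.79 (0.77–0.89 unadjusted) and disagreement in about 17–31% of trials.
- dM of 0.5–1.0 gives 0.28–0.50, power of 0.32–0.65 and disagreement in about 22–55%.
- dM of −0.5 gives 0.50–0.62.

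**5. BMI.** With height fixed over 12 weeks, change in BMI is change in body mass divided by height squared, so the covariate nearly determines the outcome. Assume an extra loss of 0.5–1.5 kg, SD 2–3 kg and mean height 1.68 m (SD 0.07–0.10 m). The unadjusted effect is −0.18 to −0.54 kg/m² (power only 0.07–0.42); the mean adjusted effect is within 0.001 of zero.

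These are change-score models, not the full three-visit model.

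**The case against.** The strongest defence is that the hierarchy is already implied. The t-test is unconditional and carries the stated power for Aims 1 and 3; the ANCOVA is conditional, and nothing says it replaces the t-test. That is the natural reading, and it limits the harm. It does not supply the missing statement of rank, nor does it correct the confounder rationale.

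Second, Section 3.1 concedes that metformin's odour prevents full blinding, so behaviour could differ between arms for reasons unrelated to pharmacology. Asking whether an effect persists at similar activity and weight change is then a fair second question. This supports keeping the model with a label. It does not make the result metformin's total effect, and weight change still cannot separate behaviour from drug.

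Third, the disagreement rates overstate bias. With no true arm difference in steps or weight there is no bias, yet the analyses still disagree in 17–18% of fired trials, because a fired trigger makes steps collinear with arm. Only the excess over that floor can be attributed to the changed target, and part of the power loss is likewise imprecision. No passage says that metformin alters steps, a chance step difference alone does not bias the steps-adjusted estimate, and the largest figures need a weight difference of 1 SD. All of this stands.

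Fourth, the unadjusted mean also moves in fired trials (0.54 in the third row of the second table), because the trigger selects on observed steps. That is true, but over all trials the unadjusted comparison remains unbiased for the total effect; the weight-adjusted one does not when weight responds to the drug and is linked to the outcome.

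Finally, this is a pilot, BMI is secondary and unpowered, and nothing says that BMI would be adjusted. These points bear on urgency, not on whether the rule is right.

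**Conclusion.** The concern holds. For outcomes driven by weight or sharing causes with it, the adjusted estimate does not target metformin's total effect, and the plan neither ranks it nor restricts its use. A1c, HOMA-IR and body composition are the plausible cases, and BMI is affected almost by construction. For an outcome unrelated to weight and steps the target is unchanged; the documents do not say which case holds for LC3 or DNA methylation.

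The size cannot be derived from the documents. Under the assumptions shown, a small extra weight loss on metformin (0.1–0.2 SD) shifts the A1c estimate by 0.01–0.04 points through the weight covariate alone. A loss of 0.5–1.0 SD shifts it by 0.06–0.20, and the direction reverses if the placebo arm loses more. The argument is strongest for change in body mass and weaker for steps.

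**What to change.** In Potential Challenges, in both Section 3.1 and Section 13.2:

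- Remove the description of an adherence difference as a confounder that the ANCOVA corrects.
- State that the unadjusted comparison in the Data Analysis paragraph of Section 3.1 is the treatment-effect estimate whatever adherence is observed.
- Report step counts and weight change by arm.
- If the ANCOVA is kept, label it supportive or exploratory and do not apply it to BMI.

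The cost is protocol wording in two places, with no new data, visits or subjects.
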